7.3.6 Other anti-diabetic agent

Subjects who used other anti-diabetic agent during the study will be summarized with number of subjects, percentages and number of cases and will be coded using the World Health Organization Anatomical Therapeutic Chemical index (WHO ATC index) latest version and will be summarized with Level 1 (anatomical main group) and Level 5 (chemical substance) using number of subjects, percentages and number of cases. However, if level 5 is 'Combinations', 'Various' or 'various combinations', then level 4 will be used instead. (If level 5 doesn't exist then a higher level will be used.) The frequency is counted as one person in each classification even if one subject use multiple other anti-diabetic agent.

7.4 ESGLITEO ADMINISTRATION STATUS

Total period of drug use, Total number of administrations, Average number of administration per day will be summarized using number of subjects, mean, SD, median, minimum, maximum, 5th percentile and 95th percentile.

In addition, the frequency and percentage of reasons for early interruption are presented when the subjects prematurely withdraw the study.

8. SAFETY ANALYSIS

Safety analyses will be performed on Safety set.

An adverse event (AE) is defined as any untoward medical occurrence in a patient or clinical investigation subject administered a medicinal product and which does not necessarily have a causal relationship with this treatment. An adverse event can therefore be any unfavorable and unintended sign (e.g. an abnormal laboratory finding), symptom, or disease temporally

CONFIDENTIAL

STATISTICAL ANALYSIS PLAN

associated with the use of a medicinal product, whether or not considered related to the medicinal product.

An adverse drug reaction (ADR) is defined as a response to a medicinal product which is noxious and unintended. Response in this context means that a causal relationship between a medicinal product and an adverse event is at least a reasonable possibility. Adverse reactions may arise from use of the product within or outside the terms of the marketing authorization or from occupational exposure. Conditions of use outside the marketing authorization include off-label use, overdose, misuse, abuse and medication errors.

ADR is defined as the case where the causal relationship with Esglito evaluated by the investigator falls under the following.

- Certain
- Probable/Likely
- Possible
- Conditional/Unclassified
- Unassessable/Unclassifiable

The following Aes are defined as serious adverse event (SAE).

- Results in death
- Is life-threatening
- Requires in-patient hospitalization or prolongation of existing hospitalization
- Results in persistent or significant disability or incapacity
- Is a congenital anomaly/birth defect
- Other medical criteria

Unexpected adverse event (UAE) means any adverse event not listed in the permit.

Adverse events of special interest (AESI) refer to any of the following cases.

CONFIDENTIAL

STATISTICAL ANALYSIS PLAN

- Hepatic injury
 - An elevation of AST and/or ALT >3-fold ULN combined with an elevation of total bilirubin >2-fold ULN measured in the same blood draw sample.
 - An isolated elevation of AST and/or ALT >5-fold ULN (without an elevation of total bilirubin >2-fold ULN)
- Decreased renal function
 - Creatinine value shows a >2-fold increase from baseline and is above the ULN
- Metabolic acidosis, ketoacidosis and diabetic ketoacidosis (DKA)
- Lower limb amputation
 - Amputation (i.e. resection of a limb through a bone)
 - Disarticulation (i.e. resection of a limb through a joint)
 - Auto-amputations (i.e. spontaneous separation of non-viable portion of the lower limb)

Not included in this definition are debridement (removal of callus or dead tissue), procedures on a stump (like stump revision, drainage of an abscess, wound revision etc.) and other procedures (e.g., nail resection or removal) without a concomitant resection of a limb (amputation or disarticulation).

Adverse events leading to discontinuation refers to all adverse events in which action taken with study drug due to AE is 'Drug withdrawn'.

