- Any changes in laboratory tests if there is any lab result which was clinically significant compared to data before Esgliteo therapy (This data is collected on the basis of medical need, i.e. independent of the NIS)
- Any adverse events noted, AESI (Adverse Event of Special interest)
- Study completion status (if necessary)

- The final effectiveness evaluation(if necessary)
- NIS physician's electronic signature for data integrity (if necessary)

9.2.3.4 Visit 3; 24 weeks from Visit 1

After 24 weeks from Visit 1, the patients will return for follow-up. The followings will be noted and recorded in the eCRF.

- Visit date
- Physical examination: body weight, blood pressure(SBP, DBP)
- Any changes of Esgliteo given
- Effectiveness endpoints: HbA1c, FPG (Within 1month prior to Visit 3)
- Renal function test: Serum creatinine, eGFR, Urine ACR if blood test result is available (The most recent data since last visit, except previously entered data)
- Concomitant anti-hyperglycemic agent including new medications taken since last visit: any changes in the concomitant medications (dose and dosing intervals)
- Concomitant medications including new medications taken since last visit: any changes in the concomitant medications (dose and dosing intervals)
- Any changes in laboratory tests if there is any lab result which was clinically significant compared to data before Esgliteo therapy (This data is collected on the basis of medical need, i.e. independent of the NIS)
- Any adverse events noted, AESI (Adverse Event of Special interest)
- Study completion status(if necessary)
- The final effectiveness evaluation
- NIS physician's electronic signature for data integrity

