9.3.3 Assessment Criteria

9.3.3.1 Assessment of safety

- Adverse events (event name/ symptoms/ sign/ identify hypoglycemia symptoms)
- Onset date, End date
- Intensity (Mild/ Moderate/ Severe)
- Serious (Serious/ Non-Serious)
- Outcome of the event (Recovered/ Not yet recovered/ Sequela/ Fatal/ Unknown)
- Causality (Certain/ Probable/Likely/ Possible/ Unlikely/ Conditional/ Unclassified/ Unassessable/Unclassifiable)
- Action taken with study drug due to AE (Dose not changed/ Dose reduced/ Dose increased/ Drug withdrawn/ Not applicable)
- Adverse Event of Special interest (Hepatic injury/ Decreased renal function/ Metabolic acidosis, ketoacidosis and diabetic ketoacidosis (DKA)/ Lower limb amputation)

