The term Adverse Event of Special Interest (AESI) relates to any specific AE that has been identified at the project level as being of particular concern for prospective safety monitoring and safety assessment within this study, e.g. the potential for AEs based on knowledge from other compounds in the same class. AESIs need to be reported to the [REDACTED] within the same timeframe that applies to SAEs.

The following are considered as AESIs:

- Hepatic injury
 - An elevation of AST and/or ALT \geq 3-fold ULN combined with an elevation of total bilirubin \geq 2-fold ULN measured at the same visit, or in samples drawn within 30 days of each other, OR
 - An elevation of AST and/or ALT \geq 3-fold ULN and INR \geq 1.5-fold ULN measured at the same visit, or in samples drawn within 30 days of each other, OR
 - An elevation of AST and/or ALT \geq 3-fold ULN with new onset, or worsening of fatigue, nausea, vomiting, right upper quadrant pain or tenderness, fever, rash, and/or eosinophilia ($>5\%$), OR
 - An isolated elevation of AST and/or ALT \geq 5-fold ULN
- Decreased renal function
 - Creatinine value shows a >2 -fold increase from baseline and is above the ULN
- Metabolic acidosis, ketoacidosis and diabetic ketoacidosis (DKA)
- Lower limb amputation
 - Amputation (i.e. resection of a limb through a bone)
 - Disarticulation (i.e. resection of a limb through a joint)
 - Auto-amputations (i.e. spontaneous separation of non-viable portion of the lower limb)

Not included in this definition are debridement (removal of callus or dead tissue), procedures on a stump (like stump revision, drainage of an abscess, wound revision etc.) and other procedures (e.g., nail resection or removal) without a concomitant resection of a limb (amputation or disarticulation).

Each lower limb amputation, disarticulation, or auto-amputation should be reported separately. The SAE report should include the date of the procedure, the level of amputation or disarticulation, the medical condition(s) leading to the procedure and if the patient had some of the known risk factor(s) for lower limb amputation.

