1. INTRODUCTION

The purpose of this statistical analysis plan(SAP) is to describe in detail the plan for statistical analysis method, processing method of data to be used for analysis, and definition of analysis datasets based on the Ministry of Food and Drug Safety's guidelines (2021.11) for final analysis of <1275-0028, 4.0, A regulatory requirement non-interventional study (NIS) to monitor the safety and effectiveness of Esgliteo (empagliflozin/linagliptin, 10/5mg, 25/5mg) in Korean patients with type 2 diabetes mellitus (T2DM), 2022.05.23>,. The table shell and list, which will record the analysis results, will be developed as a separate document. If the analysis is performed in a manner different from this document, the method of change and the reason for change will be recorded in detail in the final report.

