10.5 DETAILS OF SERIOUS UNEXPECTED AEs

The details of Serious Unexpected AEs collected from use result surveillance, special study (Pharmacoepidemiology study, etc.), clinical trials and Spontaneous reporting will be presented in a listing.

11. Changes to the planned analysis method

In the 9.7.1 demographic analysis item of Protocol (version 4.0), it is described that the administration status of this drug (average daily dose) is analyzed, but since Esglito is a composite, the average number of administrations per day will be analyzed.

[figure not shown]
12. SAS program code

The following SAS program codes will be used.

Table 6 SAS program code

Analysis method	SAS program code
Pearson's chi-square test or	PROC FREQ DATA=dataset;
Fisher's exact test	TABLE ae*factor/CHISQ EXACT; RUN;
Paired t-test	PROC UNIVARIATE DATA=dataset; VAR diff;

CONFIDENTIAL

STATISTICAL ANALYSIS PLAN

Analysis method	SAS program code
	RUN;
t-test	PROC TTEST DATA=dataset; CLASS factor; VAR chg; RUN;
ANOVA	PROC MIXED DATA=dataset; CLASS treatment; MODEL variable=treatment; LSMEANS treatment / PDIFF CL; RUN;
Simple logistic regression	PROC LOGISTIC DATA=dataset; CLASS factor; MODEL ae=factor; RUN;
Multiple logistic regression	PROC LOGISTIC DATA=dataset; CLASS factor1 factor2 factor3; MODEL ae= factor1 factor2 factor3 factor4; RUN;

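### SAP section 8 defines hepatic-injury AESIs by two narrow criteria where protocol v5.0 has four, does not declare the difference and does not say how AESIs are identified, so hepatic AESI counts can be too low

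*SAP*

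**What the plan says.** Protocol section 11.1 (v5.0) lists four hepatic-injury criteria joined by OR. In each, AST and/or ALT is at or above a multiple of the upper limit of normal (ULN):

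- 3-fold, with total bilirubin at or above 2-fold;
- 3-fold, with INR at or above 1.5-fold;
- 3-fold, "with new onset, or worsening of fatigue, nausea, vomiting, right upper quadrant pain or tenderness, fever, rash, and/or eosinophilia" above 5%;
- 5-fold, isolated, with no bilirubin condition written.

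The bilirubin and INR criteria accept values "measured at the same visit, or in samples drawn within 30 days of each other, OR".

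SAP section 8 lists two criteria: "An elevation of AST and/or ALT >3-fold ULN combined with an elevation of total bilirubin >2-fold ULN measured in the same blood draw sample" and "An isolated elevation of AST and/or ALT >5-fold ULN (without an elevation of total bilirubin >2-fold ULN".

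Section 1 of the SAP states that it was prepared "for final analysis of <1275-0028, 4.0, A regulatory requirement non-interventional study (NIS) to monitor" safety and effectiveness, giving the v4.0 date of 23 May 2022. The completion certificate names the file as v2.0 final, 19 Apr 2023. Item 8 in protocol section 5, dated 28 Oct 2022, records that the hepatic-injury definition was updated. SAP section 11 declares one change, opening "In the 9.7.1 demographic analysis item of Protocol (version 4.0"; it concerns average daily dose only.

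Protocol section 9.3.3.1 includes among the items assessed for adverse events "Adverse Event of Special interest (Hepatic injury/ Decreased renal function/ Metabolic acidosis, ketoacidosis and diabetic ketoacidosis (DKA)/ Lower limb amputation". The SAP does not mention this record when it defines AESIs.

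**The concern.** Safety is the primary objective (protocol 8.1) and AESI is a named safety endpoint (protocol 9.3.2.1). SAP Table 7 reports AESIs through tables C1, C6, C20, C22, C24 and C29. A definition narrower than the protocol's would lower the hepatic counts in all of these if a programmer applied it.

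The SAP leaves that route open. It ties adverse drug reactions to the investigator's recorded causality, and discontinuations to the recorded action of withdrawing the drug. For AESIs it names no recorded field and simply lists cases with laboratory thresholds.

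Nothing in the SAP would bring the conflict to light. Section 1 requires the final report to explain departures from the SAP, but applying the SAP's own definition is not a departure.

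**Working it through.** The study size of 600 is a regulatory requirement without statistical inputs, so there is no planned figure to reproduce. The check compares the two texts, applies them to test patterns and counts days.

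**1. Texts side by side**

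| Element | Protocol 11.1 (v5.0) | SAP 8 |
|---|---|---|
| AST/ALT 3-fold with bilirubin 2-fold | at or above; same visit or within 30 days | strictly above; same blood draw only |
| AST/ALT 3-fold with INR 1.5-fold | yes; same visit or within 30 days | absent |
| AST/ALT 3-fold with symptoms or eosinophilia | yes | absent |
| AST/ALT 5-fold, isolated | at or above; no bilirubin condition written | strictly above; not if bilirubin is above 2-fold |

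Two of the four criteria are absent and the other two are narrowed. The renal, acidosis and amputation definitions agree between the documents, so only the definition changed by amendment item 8 differs. That the SAP carries the superseded v4.0 wording is a strong inference; the v4.0 text is not shown.

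**2. Test patterns** (multiples of ULN; chosen for this check, all meeting v5.0)

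| Pattern | SAP |
|---|---|
| ALT 4, INR 1.6 | not met |
| ALT 4, new symptoms | not met |
| ALT 4, bilirubin 3, drawn 10 days apart | not met |
| ALT exactly 5.0 alone | not met |
| ALT exactly 3.0, bilirubin 3, same draw | not met |
| ALT 4, bilirubin exactly 2.0, same draw | not met |
| ALT 6, bilirubin 2.5, a week apart | missed only if the bilirubin condition covers any sample |
| ALT 4, bilirubin 3, same draw | met |
| ALT 6 alone | met |

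Result: 6 missed, 1 depends on reading, 2 met by both.

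**3. Direction.** A grid of assumed values was run through both rules, with the SAP's bilirubin condition read as covering any sample. It crossed 6 AST/ALT levels, 3 bilirubin levels, 4 sampling gaps, 3 INR levels and symptoms yes/no: 6 × 3 × 4 × 3 × 2 = 432 cells.

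- Protocol's isolated elevation read as written: 72 cells meet both definitions, 252 the protocol only, 0 the SAP only.
- Protocol's isolated elevation read as requiring bilirubin below 2-fold: 69, 243 and 3. The three SAP-only cells are one boundary case: AST/ALT 6-fold, bilirubin exactly 2.0-fold, samples 31 days apart, no symptoms.

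Cell counts show direction, not frequency.

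**4. Dates**

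- v5.0 to final SAP: 28 Oct 2022 to 19 Apr 2023 = 173 days.
- Planned data collection: 30 Oct 2021 to 30 Nov 2022 = 396 days.
- v5.0 to planned end of data collection: 28 Oct to 30 Nov 2022 = 33 days; 33/396 = 8.3%. This is a maximum, because protocol 10.1 requires approval before amendments are implemented.

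**5. Sensitivity to one case.** With assumed counts in 600 patients (exact 95% intervals), 0 cases give 0% (0 to 0.61%) and 1 case gives 1/600 = 0.17% (0.00 to 0.93%).

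**The case against.** The strongest reply is that AESIs are probably counted from site records. The category is assessed for each event, AESIs are noted at both follow-up visits, and they are reported within 24 hours. SAP Table 3 derives no AESI variable and Table 7 has no liver-laboratory table. AST, ALT, bilirubin and INR are not scheduled tests; the visit lists say of laboratory changes "This data is collected on the basis of medical need, i.e. independent of the NIS". On that reading the SAP wording removes no case. This stands as a limit: the undercount is conditional. It does not settle the matter, because no SAP sentence says that the recorded category governs, and the report would still print a definition at odds with the protocol in force when data collection was planned to end.

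Second, the SAP openly names v4.0 as its base, so section 11 may have had nothing to declare against that version. The version gap is indeed visible. The change in a safety endpoint's definition is not, and the SAP was finalised 173 days after it.

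Third, six of nine is not a rate. The patterns were constructed, and three of the six misses need exact equality with a threshold. This is accepted. The substantive gaps are the INR criterion, the symptom criterion and the 30-day window.

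Fourth, v5.0 covers at most 8.3% of planned data collection, so replacing the text alone would misdescribe how most events were categorised, and re-screening on unscheduled tests will be incomplete. Both points are right. They are reasons to report definitions by period and to state where data are lacking.

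Finally, the analyses are descriptive, hepatic events remain in the general adverse event tables, and expedited reporting follows protocol 11.2. The error concerns classification as an AESI, not whether events are captured.

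**Conclusion.** The concern holds. The current SAP and the current protocol define the same safety endpoint differently, the SAP does not declare this, and it does not say how AESIs are identified. If the SAP text is applied, the error runs towards too few hepatic AESIs, apart from one boundary case under a narrow reading of the protocol. If the recorded category is used, counts are unaffected and the fault is a printed definition that conflicts with the protocol. Most events were probably categorised under the earlier protocol version, given the planned dates.

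The number of missed cases cannot be estimated, because the documents give no hepatic-injury rate. Confidence is high for the mismatch; the undercount depends on which source the tables use. It should be fixed before the final report. No view is taken on which thresholds are clinically right; the point is that the two sections must be reconciled.

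**What to change.** 1. Cite protocol v5.0 in SAP section 1 and replace the hepatic-injury text in section 8 with the v5.0 definition.
2. State whether the AESI tables use the category recorded in the eCRF or a re-derivation from the definition.
3. Re-screen recorded hepatic adverse events, and any liver laboratory values available from before 28 Oct 2022, against v5.0. As these tests are unscheduled, this is possible only where data exist.
4. Report in SAP section 11 which definition applied in which period and where data were too sparse to classify.

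The cost is a SAP wording change and a small check of existing records, with no new data collection. The AESI count may rise slightly, and some earlier records will remain unclassifiable.

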8.1 SUMMARY OF ADVERSE EVENTS

The following types of AEs will be summarized with the number of subjects and proportion of the number of subjects with AE, number of cases and 95% exact confidence intervals.

- AE
- ADR
- SAE
- Serious adverse drug reaction (SADR)

CONFIDENTIAL

STATISTICAL ANALYSIS PLAN

- UAE
- Unexpected adverse drug reaction (UADR)
- Non-serious adverse drug reaction
- AESI
- Adverse events leading to discontinuation

8.2 ANALYSES OF ADVERSE EVENTS

The following types of AEs will be coded with MedDRA latest major version and will be summarized with SOC and PT using the number of subjects and proportion of the number of subjects with AE, number of cases. The details of SAEs will also be presented in a listing.

- AE/ADR
- SAE/SADR
- UAE/UADR
- Non-serious adverse drug reaction
- AESI
- Adverse events leading to discontinuation
- AE classified by Outcome of the event
- AE classified by Therapy for the event
- AE classified by Action taken with Esglito
- AE classified by Intensity
- AE classified by Causal relationship

In the analysis for re-examination application, the following AEs of rare (less than 0.1%) or occasional (less than 0.1%~5%) occurrence will be coded with MedDRA latest major version and will be summarized with SOC and PT using the number of subjects and proportion of the number of subjects with AE.

- SAE/SADR
- UAE/UADR

CONFIDENTIAL

STATISTICAL ANALYSIS PLAN

8.3 SAFETY ANALYSES BY FACTORS

8.3.1 Univariate analysis

The following categorical variables will be summarized using number of subjects, the number of subjects and proportion of the number of subjects with AE and 95% confidence interval. AE Occurrence will be analyzed using Pearson's chi-square test or Fisher's exact test to determine if statistically significant differences exist. (However, if [Diabetes mellitus complications] responds with [Not applicable], [Pregnancy] responds with [Not applicable], [Height] responds with [Not done], it is excluded from Pearson's chi-square test or Fisher's exact test.)

- Gender (Male, Female)
- Smoking status (Never smoked, Ex-smoked, Currently smokes)
- Family history of T2DM (Yes, No)
- Previous allergy (Yes, No)
- Diabetes mellitus complications (Retinopathy, Neuropathy, Nephropathy, Vasculopathy, Other) (Yes, No, Not applicable)
- Medical history (Yes, No)
- Comorbidities (Yes, No)
- Prior medication (Yes, No)
- Concomitant medication (Yes, No)
- Other anti-diabetic agent (Yes, No)

For the following continuous variables AE Occurrence will be summarized using odds ratio and 95% confidence interval for an increase or decrease per defined unit of the variable based on using simple logistic regression.

- Age (years)
- Height (cm)
- Weight (kg)

CONFIDENTIAL

STATISTICAL ANALYSIS PLAN

- Duration of disease (years)
- Total period of drug use (days)
- Total number of administrations
- Average number of administration per day

Subjects of special investigation will be summarized using number of subjects, number of subjects with AE, proportion of subjects with AE and 95% confidence interval. AE Occurrence will be analyzed by using Pearson's chi-square test or Fisher's exact test to confirm statistically significant differences.

- Geriatric population (65 years or more, Less than 65 years)
- Pregnant women (Yes, No, Not applicable)
- Renal impairment (Yes, No)
- Hepatic impairment (Yes, No)
- Long term use (24 weeks or more)

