9.2.3.2 Visit 1; Baseline Visit

Upon patient enrolment, the following will be recorded on the patient's eCRF.

- Visit date
- Diagnosis: date of the diagnosis of T2DM, Family history of T2DM
- Inclusion / Exclusion criteria
- Data release consent form: Date of data release consent form

Boehringer-Ingelheim**Non-interventional Study Protocol****BI Study Number 1275-0028****c37168579-01**

Proprietary confidential information © 2022 Boehringer Ingelheim International GmbH or one or more of its affiliated companies

- Demographic data: Year of birth(age), Gender, Pregnancy, Previous allergy, Height, Smoking status
- Diabetes mellitus related complication(Retinopathy, Neuropathy, Nephropathy, Vasculopathy, Others)
- Medical history: Renal impairment, Hepatic impairment, Others. (history of concomitant disease within 6 months prior to baseline)
- Physical examination: Body weight, Blood pressure (SBP, DBP)
- Renal function test: Serum creatinine, eGFR, Urine ACR if blood test result is available(the most recent data prior to baseline)
- Effectiveness assessment: HbA1c, FPG (within 1 month prior to baseline)
- Concomitant anti-hyperglycemic agent: record any anti-hyperglycemic agents that have been taken at least once (within 1 month prior to baseline)
- Concomitant medications: record all medications that have been taken at least once (within 1 month prior to baseline)
- Dose of Esgliteo given (Daily dose, Start date)

At visit 1, the patient will be requested to contact the treating physician in the event of any adverse events noted after initiating Esgliteo treatment.

9.2.3.3 Visit 2; 12 weeks from Visit 1

After 12 weeks from Visit 1, the patients will return for follow-up. The followings will be noted and recorded in the eCRF.

- Visit date
- Physical examination: Body weight, Blood pressure (SBP, DBP)
- Any changes of Esgliteo given
- Effectiveness assessment: HbA1c, FPG (Within 1month prior to Visit 2)
- Renal function test: Serum creatinine, eGFR, Urine ACR if blood test result is available (The most recent data since last visit, except previously entered data)
- Concomitant anti-hyperglycemic agent including new medications taken since last visit: any changes in the concomitant medications (dose and dosing intervals)
- Concomitant medications including new medications taken since last visit: any changes in the concomitant medications (dose and dosing intervals)

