7.3.5 Prior and concomitant medication

Prior medication is defined as any medication that the subjects took before the first dose of Esgliteo. Concomitant medication is defined as any medication that the subjects took on or after the first dose of Esgliteo.

Prior medication is any medication that can be classified into the following category.

- Medication start date < Start date of first Esgliteo administration

Concomitant medication is any medication that can be classified into the following category.

- Medication start date \geq Start date of first Esgliteo administration

Table 5 Examples of categorization

Medication start date	Medication end date	Date of first Esgliteo administration	Prior medication	Concomitant medication
2020-01-01	2020-01-14	2020-01-15	Y	
2020-01-01	2020-01-15	2020-01-15	Y	
2020-01-01	2020-01-20	2020-01-15	Y	
2020-01-01	Ongoing	2020-01-15	Y	
2020-01-15	2020-01-15	2020-01-15		Y
2020-01-15	2020-01-20	2020-01-15		Y
2020-01-15	Ongoing	2020-01-15		Y
2020-01-20	2020-01-25	2020-01-15		Y
2020-01-20	Ongoing	2020-01-15		Y

If there is a missing date, Prior/concomitant medication is classified by processing according to [6.2 Handling of Missing Dates].

Prior and concomitant medications will be summarized with number of subjects, percentages and number of cases. Prior and concomitant medications will be coded using the World Health Organization Anatomical Therapeutic Chemical index (WHO ATC index) latest version and

CONFIDENTIAL

STATISTICAL ANALYSIS PLAN

will be summarized with Level 1 (anatomical main group) and Level 5 (chemical substance) using number of subjects, percentages and number of cases. However, if level 5 is 'Combinations', 'Various' or 'various combinations', then level 4 will be used instead. (If level 5 doesn't exist then a higher level will be used.) The frequency is counted as one person in each classification (Subjects investigated with prior and concomitant medication, level 1 and level 5) even if one subject has multiple prior/concomitant medications.

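### The SAP 8.3.1 test of concomitant medication against AE occurrence counts drugs given to treat the AE, so the Table C16 comparison is contaminated by reverse causation

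*SAP*

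**What the plan says.** SAP 8.3.1 lists "Concomitant medication (Yes, No") and "Other anti-diabetic agent (Yes, No") among the categorical factors for safety. For these factors, "AE Occurrence will be analyzed using Pearson's chi-square test or Fisher's exact test to determine if statistically significant differences exist". SAP 5.2 sets the level at two-sided 5%. The results go to Table C16.

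SAP 7.3.5 defines the first factor in two ways. The sentence reads: "Concomitant medication is defined as any medication that the subjects took on or after the first dose of Esgliteo". The operational rule below it requires a start date on or after the first Esgliteo date, and Table 5 puts a drug started earlier and still ongoing under prior medication only.

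For the second factor, SAP 7.3.6 has no start-date rule: "Subjects who used other anti-diabetic agent during the study will be summarized".

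On data capture, Protocol 9.1.3 asks for all concomitant medication up to the final follow-up visit. The Visit 2 and Visit 3 pages (Protocol 9.2.3.3 and 9.2.3.4) ask for "Concomitant medications including new medications taken since last visit: any changes in the concomitant medications (dose and dosing intervals"), with a parallel item for anti-hyperglycaemic agents. SAP 8.2 tabulates "AE classified by Therapy for the event" (Table C10), so treated AEs are expected.

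**The concern.** A patient on no other medicine who has an infection and receives an antibiotic becomes a Yes for concomitant medication because of the AE. A patient given a new or replacement glucose-lowering drug because of an AE may become a Yes for other anti-diabetic agent in the same way. The test then compares AE occurrence between Yes and No. The only exclusions in 8.3.1 are for answers of not applicable or not done. No rule requires the drug to start before the event, and none sets aside drugs given for it.

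The bias has a known direction: any AE treated with a newly started drug pushes the odds ratio above 1. Table C16 could therefore show co-medication as a risk factor for AEs when it has no effect, and the report could explain an artefact as a finding.

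**Working it through.** The plan states no figure to reproduce. The 600 patients are a regulatory number, with no AE rate, effect size or power. The sizes below are illustrations under a true null.

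**Inputs.** From the documents: N = 600 (Protocol 9.5) and a two-sided 5% test (SAP 5.2). Assumed: AE risk p = 10-20%; share b who start a drug for reasons unrelated to an AE = 20-40%; share t of AE patients given a drug for the AE = 20-40%.

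**Formulas.**
- P(Yes | no AE) = b
- P(Yes | AE) = q = 1 − (1 − b)(1 − t)
- Odds ratio = [q/(1 − q)] / [b/(1 − b)]
- Rejection rate: two-sided normal approximation comparing q in 600p patients with b in 600(1 − p), pooled variance under the null.

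**Concomitant medication, start-date reading.**

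| b | t | q | Odds ratio | Rejection, p = 10% | Rejection, p = 20% |
|---|---|---|---|---|---|
| 0.2 | 0.2 | 0.36 | 2.25 | 78% | 94% |
| 0.2 | 0.4 | 0.52 | 4.33 | >99% | >99% |
| 0.4 | 0.2 | 0.52 | 1.625 | 43% | 66% |
| 0.4 | 0.4 | 0.64 | 2.67 | 95% | >99% |

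Lowest case (p = 0.1, b = 0.4, t = 0.2): the groups are 60 and 540 and the difference is 0.52 − 0.40 = 0.12. The pooled proportion is 0.412, the null SE √(0.412 × 0.588 × (1/60 + 1/540)) = 0.0670, and the alternative SE √(0.52 × 0.48/60 + 0.40 × 0.60/540) = 0.0679. Then (0.12 − 1.96 × 0.0670)/0.0679 = −0.17, which gives 43%.

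Highest odds ratio (p = 0.2, b = 0.2, t = 0.4): of 120 AE patients 62.4 are Yes, and of 480 others 96 are Yes. Apparent AE risk is 62.4/158.4 = 39% with the factor and 57.6/441.6 = 13% without it.

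A simulation over wider inputs (p 10-30%, b 20-50%, t 10-50%; 2,000 runs each) gave odds ratios of 1.22 to 6.00 and rejection in 13% to 100% of runs.

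**Concomitant medication, sentence reading.** If ongoing background drugs count, b rises. With assumed b = 0.7-0.9 and p = 10-20%:
- t = 0.2: odds ratio 1.28 to 1.36, rejection 6% to 25%
- t = 0.4: odds ratio 1.74 to 1.95, rejection 12% to 77%

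**Other anti-diabetic agent.** Assumed p = 10-30%, background use 30-60%, and 5-20% of AE patients given such an agent because of the AE: odds ratio 1.09 to 1.83, simulated rejection about 6% to 92%. Example (20%, 30%, 10%): q = 1 − 0.7 × 0.9 = 0.37; odds ratio (0.37/0.63)/(0.30/0.70) = 1.37; apparent AE risk 23.6% against 18.4%; rejection 32%.

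**After the fix.** With the factor set before any AE can act on it, q = b and the odds ratio is 1. The same simulated data gave rejection in 4.1% to 5.7% of runs, which is 5% within simulation error.

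**The case against.** The strongest reply is that little rests on these tests. The primary objective is to monitor the safety profile. It is answered by the AE counts, proportions and exact intervals of SAP 8.1, which this issue does not touch. The protocol abstract calls all analyses descriptive, and Protocol 9.9.3 already concedes residual confounding. That stands as a limit on the consequence. It does not answer the point, because 9.9.3 does not mention reverse causation and the SAP still tests for significance.

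A reader might call the comparison circular. That goes too far: same-day co-prescriptions and later drugs unrelated to any AE also count, so the factor is contaminated and not determined by the outcome.

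A reader might also cite the protocol's request to identify influencing factors and to describe the meaning of significant ones. That wording belongs to the logistic regression item of Protocol 9.7.2. These two factors implement the preceding chi-square/Fisher item. SAP 8.3.2 selects from simple logistic regression, which 8.3.1 assigns to continuous variables, while the Table 6 code has a CLASS statement. Entry of either factor into the multivariable model is unclear and cannot be assumed.

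Finally, the two factors should not be treated as equally affected. Background therapy dilutes the other-agent factor. The documents do not say how often an AE leads to a new agent, or settle whether a replacement started after Esgliteo stops is recorded. These objections stand and are reflected in the verdict.

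**Conclusion.** The point holds for concomitant medication. As operationalised, the factor contains only drugs started on or after the first dose, AE treatments are among them, and no rule removes them. The spurious odds ratio is 1.6 to 4.3, with rejection in 43% to over 99% of studies, under the assumed rates and the start-date reading. Under the sentence reading the bias remains but is smaller. Other anti-diabetic agent has the same weakness to a lesser degree (about 1.1 to 1.8), and that range depends wholly on an unstated rate of AE-driven additions or switches.

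The documents do not support the wider inference that the primary safety results are biased: AE incidence is unaffected, and the demonstrated consequence is a misleading comparison in Table C16. It should be corrected because safety is the primary objective and the remedy is cheap.

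**What to change.** For the factor tests in SAP 8.3.1, set concomitant medication and other anti-diabetic agent to Yes only if the drug was in use on the day of first Esgliteo administration: started on or before that day, and ended on or after it or ongoing. A later start does not set the factor to Yes. Report later-started drugs descriptively in Tables B7 and B8. Reconcile the 7.3.5 sentence with its start-date rule and Table 5. Record the change in SAP section 11.

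For consistency, use the same definition in SAP 9.2 item 4 and 9.4, where drugs added after poor response could create a similar bias. This part is secondary and not quantified.

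The costs should be stated:
- True exposure to a drug added later but before an AE is no longer counted.
- The factor overlaps heavily with prior medication, already in 8.3.1; it differs by requiring use on the first-dose day and by admitting same-day starts.
- Counts will differ from Tables B7 and B8, which needs a footnote.
- Table 2 imputes an unknown start day to the first of the month, so a drug begun later in the month of first dose could be classed as in use at that dose. This also needs a footnote.

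No new data are needed: SAP 6.2 and 7.3.5 already work from start and end dates.
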